A number of quantitative and semi-quantitative imaging biomarkers for each tracer will be computed at each imaging time point, and the change in each biomarker between time-points will also be computed. These data will be compared with clinical endpoints (standard RANO criteria, survival, time to progression), and with tumor biologic information (histology, WHO grade, vascularity, MIB-1, VEGF, EGFR, p53, IDH status) in cases when tumor tissue becomes available from standard care. These preliminary and exploratory data will provide information regarding semi-quantitative changes in uptake consistent with standard response, the potential value of concurrent multiple PET biomarkers for predicting tumor behavior prior to the start of therapy, for improved prognostication, for more efficient and effective tumor surveillance, and/or for more appropriate assignment of patients to conventional, aggressive, or investigational therapies early in their clinical courses. This initial data will be important for design of subsequent clinical trials using [F]Fluciclovine and/or [F]FLT to assess response to chemoradiation in high-grade primary brain tumor.

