## **1.2. The Hypotheses to be Tested and Objectives**

The hypothesis of this exploratory clinical trial in patients with high-grade a primary brain tumor who receive chemoradiation is that the PET imaging agents [F]Fluciclovine and/or [F]FLT will be a better predictor of tumor response than standard MRI based brain tumor response criteria. When used in conjunction, the two PET agents may be better able to predict tumor aggressiveness and thus overall survival than the use of individual-tracer PET biomarkers. This may eventually lead to improved assessment of response (including time to progression and overall survival) and differentiation of tumor recurrence/progression from treatment effect (pseudoprogression).

The primary endpoint of the study is that a 25% reduction in  $SUV_{max}$  or  $SUV_{mean}$  for each of the PET imaging tracers will be predictive of increased overall survival.

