## 4. RATIONALE, GOALS AND OBJECTIVES

### 4.1. Clinical Rationale

The standard treatment approach for patients with high-grade primary brain tumors includes maximum feasible surgical resection, followed by 6 weeks of concurrent cranial irradiation, and daily low-dose temozolomide chemotherapy; followed by 12 cycles of high-dose temozolomide administered for 5 consecutive days every 4 weeks (Stupp et al., 2005). Contrast-enhanced MRI is the current standard for evaluating the success of therapy and monitoring for tumor recurrence. MRI is typically obtained prior to initial surgery, within 24 hours after surgery, at the conclusions of cranial irradiation, and then every 8 weeks during temozolomide chemotherapy until evidence of recurrence. Despite this careful clinical and radiographic surveillance, and despite decades of research into the histologic and molecular classification of primary brain tumors, our ability to predict tumor behavior remains very limited. Some gliomas will result in overall survival times of only months, whereas other histologically-identical gliomas may yield survivals of years to decades (Curran et al., 1993, Carson et al., 2007). Current assessment of tumor response to therapy is also poor. Patients with complete radiographic response after cranial irradiation often progress rapidly post-irradiation. In contrast, some patients with enhancing masses at the end of chemoradiotherapy may respond dramatically to further chemotherapy alone; or the masses may even disappear in the absence of further therapy, so called “tumor pseudoprogression” (Chamberlain et al., 2007). This confounding situation demonstrates a need for better assessment of tumor response.

Improvements in the ability to predict tumor behavior prior to the start of therapy would allow more efficient and effective tumor surveillance; better prognostication; and more appropriate assignment of patients to conventional, aggressive, or investigational therapies early in their clinical courses. This would provide huge economic and social benefits, and could afford decisive insights into brain tumor physiology and biology. Similarly, the ability to identify, earlier and more accurately, whether individual patients were responding to therapy would allow prompt discontinuation of ineffectual treatments and institution of potentially more effective therapies.

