### Secondary Exploratory Objectives

No multiple comparison adjustment will be performed for analysis of secondary endpoints.

- Assess the association between overall survival and change in each of the following quantitative markers for [F]Fluciclovine and [F]FLT:  $K_1-k_4$ ,  $K_{net}$  and  $K^{trans}$ , from baseline to post therapy. This association will be addressed by Kaplan-Meier curves and associated logrank tests. Cox proportion hazards regression will be used to estimate hazard ratios.
- Assess the association between progression free survival and change in each of the following quantitative markers for [18F]Fluciclovine and [18F]FLT:  $K_1-k_4$ ,  $K_{net}$  and  $K_{trans}$ , from baseline to post therapy. This association will be addressed by Kaplan-Meier curves and associated logrank tests. Cox proportion hazards regression will be used to estimate hazard ratios.
- Assess the ability of [F]FLT and/or [F]Fluciclovine alone or together to predict true progression from pseudoprogression in patients with this clinical dilemma. True progression will be separated from pseudoprogression by subsequent MRI imaging. Receiver operating characteristic curve (ROC) analysis with true progression as outcome and each imaging marker or best combination as predictor will be used for this assessment. Bootstrap methods will be used to assess the standard error.
- A 25% reduction in  $SUV_{max}$  or  $SUV_{mean}$  for each of the PET imaging tracers will be more predictive of longer overall survival, than the current MRI based response criteria. This endpoint will be addressed by informal comparison of Kaplan-Meier curves, log rank p-values, and hazard ratios from separate analyses of overall survival for each imaging parameter.
- A 25% reduction in  $SUV_{max}$  or  $SUV_{mean}$  for each of the PET imaging tracers will be more predictive of time to progression than the current MRI based response criteria. This endpoint will be addressed by informal comparison of Kaplan-Meier curves, log rank p-values, and hazard ratios from separate analyses of time to progression for each imaging parameter.

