With an initial sample size of 30, we estimate that approximately 75% of the subjects (N = 22) will have both a [F]Fluciclovine-PET and [F]FLT-PET after completion of initial chemoradiotherapy. Our justification of sample size is based on data on the prediction of OS using PET reported in Chen et al. (Chen et al., 2007). In this study more than 25% reduction in tumor [F]FLT uptake as measured by standardized uptake value was defined as a metabolic response. In this study there were nine responders (47%) and 10 non-responders (53%). Responders survived three times as long as non-responders (10.8 v 3.4 months;  $P = .003$ ), and tended to have a prolonged progression-free survival ( $P = .061$ ). Both early and later [F]FLT - PET responses were more significant predictors of overall survival (1 to 2 weeks,  $P = .006$ ; 6 weeks,  $P = .002$ ), compared with the MRI responses ( $P = .060$  for both 6-week and best responses). In univariate and multivariate Cox regression analysis, lack of FLT reduction at 6 weeks was the best predictor of reduced OS, with adjusted hazard ratio = 4.955 ( $p = 0.02$ ). Assuming 50% of subjects are metabolic responders, median survival of 3.4 months in non-responders and two years of follow up, a sample size of N = 22 subjects with follow up PET scans will provide 85% power to detect a hazard ratio of 4.9 using a two-sided logrank test at the 0.0125 significance level.

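### Section 7.2 compares PET with MRI only by setting separate analyses side by side, so the PET-MRI difference has no interval and the pairing within patients is ignored

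*Combined protocol and SAP*

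**What the plan says.** Section 7.2 (Secondary Exploratory Objectives) ends with two comparative statements: a 25% reduction in SUVmax or SUVmean, for each tracer, will predict overall survival better than current MRI-based response criteria, and will do the same for time to progression. The method for the first is "informal comparison of Kaplan-Meier curves, log rank p-values, and hazard ratios from separate analyses of overall survival for each imaging parameter". The method for the second is "informal comparison of Kaplan-Meier curves, log rank p-values, and hazard ratios from separate analyses of time to progression for each imaging parameter".

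The general hypothesis in sections 1.2 and 4.2 is comparative too: the PET agents "will be a better predictor of tumor response than standard MRI based brain tumor response criteria".

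No other section supplies a paired PET-MRI contrast, a model or index that compares the two markers directly, or an interval for the difference. The only bootstrap in section 7.2 belongs to the ROC objective on pseudoprogression. The sample size in section 7.3 covers only the log-rank test of PET response against survival. The plan calls these objectives secondary and exploratory, and calls the comparison informal.

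**The concern.** Whether one marker predicts better than another is a question about a difference. Two p-values, or two hazard ratios from separate fits, do not answer it. A p-value below 0.05 for PET and above 0.05 for MRI is compatible with two equally good markers, and nothing in the planned output would tell the reader so. Because both markers are read in the same patients, their estimates are correlated, and separate analyses discard that information.

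Section 7.3 shows how such output tends to be read. Summarising a cited study of 19 patients (9 responders, 10 non-responders), it says that FLT "PET responses were more significant predictors of overall survival" than MRI responses, on P = .006 and .002 against P = .060. A report of this trial could make the same step. Section 1.1 says the data will inform the design of later trials, so an unsupported ranking of PET over MRI, or of MRI over PET, could be carried forward.

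**Working it through.** **Inputs from the plan (section 7.3).** N = 22 with follow-up PET; 50% metabolic responders; "median survival of 3.4 months in non-responders and two years of follow up"; hazard ratio (HR) 4.9; two-sided alpha 0.0125. The cited medians, 10.8 and 3.4 months, give a smaller HR of 10.8/3.4 = 3.2 under exponential survival. Accrual is 8-10 patients a year to 30 (section 5.1), so 30/10 × 12 = 36 to 30/8 × 12 = 45 months.

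**The plan's own figure.** Schoenfeld's power is Φ(√d × ln HR / 2 − 2.498), where d is the number of deaths. With 11 patients per group, the accrual above and 24 months' minimum follow-up, d is 19.9 to 20.2 and power is 85.2% to 85.8%. The stated 85% reproduces. With exactly 24 months for every patient, d = 17.9 and power is 80.5%. The plan states no power or precision for PET against MRI.

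**The cited p-values, compared directly.** P = .002 and .060 correspond to z = 3.09 and 1.88, a difference of 1.21. The difference has standard error √(2(1 − ρ)), where ρ is the correlation between the two statistics, which the documents do not give.
- ρ = 0: 1.21/1.414 = 0.86, p = 0.39.
- ρ = 0.7: 1.21/0.775 = 1.56, p = 0.12.

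This approximate test would not show PET superior to MRI.

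**Illustration for this trial.**
- Hazard = h0 × exp(b1 × PET non-response + b2 × MRI non-response), with exponential survival.
- b1, b2 and h0 are solved so that each marker alone has HR 4.9 (or 3.2) and PET non-responders have a median of 3.4 months.
- Follow-up is 24 months for all.
- Assumed, not from the documents: 50% MRI responders, MRI as strong as PET, and PET-MRI agreement of 65%, 80% or 90%. With 50/50 margins these are correlations of 2 × 0.65 − 1 = 0.3, 0.6 and 0.8.
- 20,000 trials per setting; a log-rank result in the wrong direction counts as p = 1.

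| Markers equal, N = 22 | HR 4.9 | HR 3.2 |
|---|---|---|
| PET < 0.05, MRI not | 6-13% | 11-21% |
| MRI < 0.05, PET not | 6-13% | 10-20% |

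Ranges run over the three agreement levels. The smaller p-value belongs to PET in about 45-51% of trials, so there is no tilt toward PET. Simulated power for PET at 0.0125 is 68-74% in this set-up, partly because the responder split is random. With both markers at HR 6.5 (power 76-86%), PET alone is below 0.05 in 3-10% of trials.

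**What a direct contrast would deliver.** With SE(log HR) ≈ 2/√d for each marker and d = 20, the SE of the difference in log HR is √(2(1 − ρ)) × 0.447.
- ρ = 0: 0.632, so the 95% interval for the ratio of HRs is ×/÷ exp(1.96 × 0.632) = 3.45.
- ρ = 0.7: 0.346, so ×/÷ 1.97.

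For the paired difference in concordance index (2,000 trials, 1,000 resamples each), the average 95% half-width is 0.07-0.15 with equal markers. The interval lies wholly on the PET side in at most 3% of those trials.

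**The case against.** The strongest reply is that these objectives are exploratory, the comparison is openly labelled informal, and section 4.3 leaves formal hypotheses to later phase II/III trials. That stands and lowers the weight of the point. It does not remove it, because an exploratory comparison still needs its uncertainty shown.

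A second reply is that the remedy changes little. Suppose PET response truly had HR 4.9 and MRI response HR 2.0 (assumed). The concordance interval would then lie wholly on the PET side in only about 22-28% of trials, at agreement 65% or 80%. The normal approximation for the ratio of HRs is kinder, at 29-74% over ρ = 0 to 0.7. This is conceded, and it is the reason to print the interval.

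Some stronger readings are tempting but not supported:
- **That the plan gives no estimate at all.** Point hazard ratios are reported for each marker. What is missing is the interval for the contrast, and the pairing.
- **That large p-value gaps show the size of the problem.** With equal markers, p-values differ at least 10-fold in 31-58% of trials at HR 4.9. About 65-80% of those gaps occur when both p-values are below 0.05, so they overstate how often a reader would be misled.
- **That the time-to-progression comparison is circular.** The sentence "True progression will be separated from pseudoprogression by subsequent MRI imaging" belongs to the ROC objective. Section 4.1 says "Contrast-enhanced MRI is the current standard for evaluating the success of therapy and monitoring for tumor recurrence", but that describes standard care, and the section also mentions clinical surveillance. Section 1.1 merely lists "clinical endpoints (standard RANO criteria, survival, time to progression" together. Time to progression is never defined, so dependence on MRI is plausible but inferred. If present, it may favour MRI, against the trial's hypothesis.
- **That the hypothesis in sections 1.2 and 4.2 is left untestable.** That hypothesis is worded for tumor response, whereas these objectives concern survival and progression.
- **That section 7.3 relies on separate p-values alone.** It also reports a multivariate Cox result for FLT from the cited study (adjusted HR 4.955, p = 0.02).

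**Conclusion.** The point holds in limited form. For two secondary exploratory objectives, the planned method cannot show whether an apparent difference between PET and MRI is compatible with zero. With equally good markers, the display would put one below 0.05 and the other not in about 6-13% of trials in each direction at HR 4.9, and about 10-21% in each direction at HR 3.2. The method is noisy and not biased toward PET.

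These figures rest on assumed MRI strength, MRI response rate and PET-MRI agreement. The 65% agreement end at HR 4.9 is extreme, since it implies a 25-fold hazard between patients who fail on both markers and those who respond on both; at 90% agreement it is 6.4-fold. No simulation was run for time to progression. The primary analysis is unaffected, and the change is a cheap improvement to a secondary analysis.

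**What to change.** In section 7.2, for patients with both PET and MRI response, replace the informal comparison for overall survival with the paired difference in concordance index, PET response minus MRI response. Do this for each tracer and SUV measure (2 × 2 = 4 differences). Resample patients, recompute both indices in each resample, and report the bootstrap 95% interval. State that this is estimation only, and that PET will not be called more predictive than MRI on the basis of separate p-values or hazard ratios.

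For time to progression, report the same paired estimate as descriptive. Note that, to the extent that progression is determined by MRI, the comparison is not independent of MRI response and may favour MRI.

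The cost is a few sentences and a short computation on data already collected. Intervals will be wide at N = 22, so conclusions will be modest.

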### 5.5.2. Multi-Tracer PET Exams

Multi-tracer PET exams of [F]FLT and [F]Fluciclovine will be acquired in each patient at up to three time points: (1) prior to any tumor-directed therapy, either prior to surgery or after surgery providing a complete surgical resection was not performed and confirmed by a post-operative contrast MRI scan where residual tumor  $\geq 1.0$  cm in diameter was present and prior to any tumor-directed therapy; (2) within 1-4 weeks after the conclusions of the initial (~6-8 weeks) chemoradiotherapy; and (3) patients with MRI-documented possible recurrence/progression versus treatment effect (pseudoprogression) within 6 months from the time of completion of chemoradiation. The abnormality must be  $\geq 1.0$  cm in diameter by contrast MRI or CT or show changes on non-enhancing MRI sequences (T2 or FLAIR).

Patients who were originally not enrolled to study baseline and conclusion of therapy imaging will be eligible to participate at the time of MRI-documented possible recurrence/progression versus treatment effect (pseudoprogression) within 6 months from the time of completion of chemoradiation. The abnormality must be  $\geq 1.0$  cm in diameter by contrast MRI or CT or show changes on non-enhancing MRI sequences (T2 or FLAIR).

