#### Primary Endpoint

The primary endpoint of the study is that a 25% reduction in  $SUV_{max}$  or  $SUV_{mean}$  for each of the PET imaging tracers will be predictive of increased overall survival. These endpoints will be analyzed by

Kaplan-Meier analysis and logrank tests. Cox proportional hazards regression will also be used to estimate hazard ratios. Each analysis will be performed at the two sided 0.0125 significance level to adjust for four comparisons.

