### **Multi-Tracer PET Imaging Visit:**

Imaging of the two PET tracers will be performed on separate days. The two days of imaging will be scheduled according to scanner and cyclotron availability, and all days of imaging will be obtained within one to two weeks of each other.

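### The secondary progression analyses set no landmark at scan 2 and no rule for patients already called progressive by then, so the end-of-chemoradiation MRI may supply both the MRI predictor and the event

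*Combined protocol and SAP*

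**What the plan says.** The primary endpoint in Section 7.2 is that a 25% reduction in SUV "will be predictive of increased overall survival". Two of the secondary objectives concern progression:

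- **Kinetic markers:** "Assess the association between progression free survival and change in each of the following quantitative markers", with change taken from baseline to post therapy. The methods are Kaplan-Meier, log-rank and Cox.
- **PET against MRI:** a 25% SUV reduction will be "more predictive of time to progression than the current MRI based response criteria". This is to be judged by "informal comparison of Kaplan-Meier curves, log rank p-values, and hazard ratios from separate analyses of time to progression for each imaging parameter".

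The first uses progression-free survival and the second time to progression. Neither is given a time origin, event definition, assessor or censoring rule. A confirmation rule appears only under the ROC objective: "True progression will be separated from pseudoprogression by subsequent MRI imaging".

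On timing, Section 5.5.2 places the second PET examination "within 1-4 weeks after the conclusions of the initial (~6-8 weeks) chemoradiotherapy". Appendix B adds that the tracers are imaged on separate days and that "all days of imaging will be obtained within one to two weeks of each other". Section 4.1 says MRI is typically obtained "at the conclusions of cranial irradiation, and then every 8 weeks during temozolomide chemotherapy until evidence of recurrence", and it names contrast MRI as the current standard for monitoring recurrence.

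**The concern.** A predictor measured at scan 2 can only predict what happens after scan 2. A patient must be alive to have that scan, but may already have been called progressive. Nothing in Section 7.2 removes such patients or says how they are handled.

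Two effects follow if their events are counted. A patient called progressive on the end-of-irradiation MRI would be an MRI non-responder and have the event on the same image, so MRI response would appear to predict progression through shared data. A tumour that has already grown may also tend to show no fall in uptake, so PET non-response would partly record progression that came before it.

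The effects are unequal, and the planned comparison sets p-values and hazard ratios from separate analyses side by side. The distortion would therefore enter it directly, mostly against the trial's own hypothesis that PET predicts better than MRI. The rule would also have to be chosen after the data are seen.

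**Working it through.** **The plan's own figure.** None is stated for progression. The only power figure (Section 7.3) is 85% for overall survival, with N = 22, hazard ratio 4.9, two-sided 0.0125, 50% responders and a median of 3.4 months in non-responders. Schoenfeld's formula is power = Φ(√(E/4) · ln HR − z). With 36 months of accrual (30 patients at 10 a year) plus 24 months of follow-up, E = 19.9 events, and √(19.9/4) × ln 4.9 − 2.498 = 3.54 − 2.50 = 1.05, so power is 85%. It reproduces on that reading. With a fixed 24 months per patient, E = 17.9 and power is 80.5%. Neither result bears on progression.

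**Timing.** Scan 2 falls 6 + 1 = 7 to 8 + 4 = 12 weeks after the start of chemoradiotherapy. The MRI at the end of irradiation can fall at or before it.

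**Inputs to the null check.** From the plan: N = 22, with half of patients non-responders on each marker. Assumed, because the documents do not give them:
- q, the share called progressive by scan 2, counted as events at that time and classed as MRI non-responders;
- c, the share of those patients who are PET non-responders (concordance);
- later progression unrelated to either marker, with median 4, 6 or 9 months and 24 months of follow-up after scan 2;
- nominal two-sided 5%.

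**By hand, q = 20%, median 6 months.**
- Early events: 22 × 0.20 = 4.4.
- Their log-rank excess in the non-responder group is 4.4 × (c − 0.5). This is 2.2 for MRI (c = 1), 1.32 for PET at c = 80%, and 0 at c = 50%.
- Variance of the tied early events: 4.4 × 0.25 × 17.6/21 = 0.92.
- Later events: 17.6 × (1 − 2^−4) = 16.5.
- MRI: the later non-responder share is 6.6/17.6 = 0.375, so variance is 0.92 + 16.5 × 0.375 × 0.625 = 4.79. The shift is 2.2/2.19 = 1.00, and rejection is about Φ(−0.96) + Φ(−2.96) = 17%.
- PET at 80%: the share is 7.48/17.6 = 0.425, so variance is 4.95. The shift is 0.59, and rejection is about 9%.

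**By simulation** (40,000 trials per setting). Results run higher than the hand calculation, because group sizes vary and the log-rank test is slightly liberal at this N. False-positive rates at nominal 5%:

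| q | MRI | PET c=50% | c=70% | c=80% | c=90-100% | With landmark |
|---|---|---|---|---|---|---|
| 0 | 6% | 6% | 6% | 6% | 6% | 6% |
| 10% | 10% | 6% | 7% | 7-8% | 8-10% | 6-7% |
| 20% | 21-22% | 6-7% | 9-10% | 12% | 16-22% | about 7% |
| 30% | 42-43% | 7% | 13% | 20% | 30-43% | 7-8% |

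The assumed later median hardly matters.

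**What drives it.** Moving every patient's origin by the same interval leaves the log-rank test unchanged. The inflation comes from keeping patients who progressed by scan 2.

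**Cost of excluding them.** 22 × 0.80 = 17.6 and 22 × 0.70 = 15.4 patients remain. Borrowing the overall survival medians and a hazard ratio of 4.9 with a fixed 24 months, purely as illustration, events fall from 17.9 to 14.3 and 12.5. Schoenfeld power falls from 91.9% to 85.2% and 80.2% at two-sided 0.05, or from 80.5% to 69.4% and 62.3% at 0.0125.

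**The case against.** The best defence is that the plan is silent, not wrong. A reader might infer that progression is defined by MRI and that early calls do count as events. Neither is written. Time to progression is undefined, and Table 3 lists it beside clinical as well as radiographic response. Section 4.3.1 gives scan 2 a forward-looking purpose: to separate tumours that will progress rapidly from those that will not. Sections 1.1 and 5.5.2 treat an MRI change within six months of chemoradiation as possible progression or treatment effect that triggers a third scan, and do not call it an outcome event. The size rests entirely on q and c. These analyses are also exploratory and unadjusted, and the PET-versus-MRI comparison is expressly informal.

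Most of this stands, and it limits the claim: early events are not excluded and may count. It does not answer the point. A stated purpose is not an analysis rule, and the named methods, run on all patients with a second scan, would include early progressors unless someone decides otherwise.

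A reader might also want overall survival restarted at scan 2. No benefit has been shown, since everyone with a scan-2 value was alive at that scan. Nor do the documents support resting the PET-versus-MRI claim on overall survival alone, which would drop a stated objective.

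**Conclusion.** The point holds for the two secondary progression objectives. They relate predictors known only at about scan 2 to progression, with no landmark and no rule for patients already called progressive. If those events are counted, the MRI association is inflated. The PET association is inflated too where early progressors are mostly PET non-responders. At an assumed 20% progressed, false positives are about 21-22% for MRI, and 9-10% to 22% for PET as concordance rises from 70% to 100%, against about 7% with a landmark.

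These figures rest on shares that the documents do not give. With no early progressors the problem vanishes, and at 50% concordance PET is not inflated. It would go too far to say that the comparison favours MRI by construction: that requires MRI-defined progression and counted early events, which are a reasonable inference and an open possibility respectively. The primary overall survival test is not affected. The change should be made before analysis, because these results are meant to inform later trials.

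**What to change.** For the progression analyses only:

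1. Set one landmark date per patient, for example the later of the two post-therapy tracer scans, since the tracers may be imaged up to two weeks apart.
2. Define progression and its assessor. Fix the MRI response assessment at or before the landmark, and keep that MRI out of the outcome.
3. Count only progression or death after the landmark. Use progression-free survival (progression or death) in both objectives.
4. Leave patients called progressive by the landmark out of the main progression analysis, judged only on information available then, and report them separately. Later MRI must not decide who is in the landmark set, because membership would then depend on the future.
5. Add a sensitivity analysis that counts post-landmark progression only when later MRI confirms it, extending the rule now given for the ROC objective.
6. Keep the PET-versus-MRI progression objective, and leave the overall survival analysis as it is.

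The cost is analysis-plan wording and lower precision: about 15-18 of 22 patients remain if 20-30% have progressed. No new data collection is needed beyond recording the dates and calls already generated in care.
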